#### **6.4. Drug logistics and accountability**

All study drugs (Icosapent ethyl/Placebo) will be stored at the investigational site in accordance with Good Clinical Practice (GCP) and Good Manufacturing Practices (GMP) requirements and the instructions given by the clinical supplies department of the Institution and will be inaccessible to unauthorized personnel.

#### **6.5. Accountability**

The investigator, or a responsible party designated by the investigator, must maintain a careful record of the inventory and disposition of the agent (investigational or free of charge) using the NCI Drug Accountability Record or another comparable drug accountability form. (See the CTEP website at <http://ctep.cancer.gov/protocolDevelopment> for the “Policy and Guidelines for Accountability and Storage of Investigational Agents” or to obtain a copy of the drug accountability form.)

#### **6.6. Destruction and Return**

At the end of the study, unused study medication (Icosapent ethyl/Placebo) should be destroyed according to institutional policies.

#### **Treatment compliance**

An adequate record of receipt, distribution, and return of all study drugs (Icosapent Ethyl/Placebo) must be kept in the form of a Drug Accountability Form.

Subject compliance with the treatment and protocol includes willingness to comply with all aspects of the protocol, and to have blood collected for all safety evaluations. At the discretion of the principal investigator, a subject may be discontinued from the trial for non-compliance with follow-up visits or study drug.

#### **6.7. Prior and concomitant therapy**

All medication that is considered necessary for the subject’s welfare, and which is not expected to interfere with the evaluation of the study treatment, may be given at the discretion of the investigator.

All medications (including contrast media) taken within 2 weeks prior to the start of the study and during the study must be recorded in the subject’s source documentation and in the CRF (including start/stop dates, dose frequency, route of administration, and indication). Specific caution should be taken when considering or administering a concomitant medication that is metabolized by the cytochrome enzymes CYP2C8, CYP2B6 and CYP2C9. Such concomitant medication should be avoided, if possible.

Permitted concomitant therapy includes:

- Standard therapies for concurrent medical conditions.
- Supportive care for any underlying illness.
- Palliative radiation therapy is allowed if the target lesion(s) are not included within the radiation field and no more than 10% of the bone marrow is irradiated.
- Granulocyte colony-stimulating factor (G-CSF) and other hematopoietic growth factors may be used in the management of acute toxicity, such as febrile neutropenia, when clinically indicated or at the investigator's discretion. However, they may not be substituted for a required dose reduction. Subjects are permitted to take chronic erythropoietin.
- Treatment with nonconventional therapies (such as acupuncture), and vitamin/mineral supplements are permitted provided that they do not interfere with the study endpoints, in the opinion of the investigator.
- Bisphosphonates
- Subjects who are therapeutically treated with an agent such as warfarin or heparin will be allowed to participate provided that their medication dose and INR/PTT are stable. Close monitoring (day 5 of cycle 1 and day 1 of each cycle) is mandatory. If either of these values are above the therapeutic range, the doses should be modified and the assessments should be repeated weekly until they are stable.

The following are not permitted:

- Other investigational treatment during or within 30 days before starting study treatment
- Systemic antitumor therapy, including cytotoxic therapy, signal transduction inhibitors, immunotherapy, and hormonal therapy
- Bone marrow transplant or stem cell rescue
- Use of any herbal remedy (e.g. St. John's wort [Hypericum perforatum])
- Please note: Patients should be seen frequently / early during treatment as per Prescribing Information
- Monitor blood pressure weekly for the first 6 weeks of treatment and every cycle or more frequently as clinically indicated.

## 7.0. Outcome Measures/Planned Assessments

### 7.1. Timing of assessments

ASSESSMENTS	Table 4. Study assessments for Icosapent ethyl/Placebo.									
	Baseline	Day 8* (± 3)	Day 15* (± 3)	Day 21* (± 3)	Day 29 (± 3)	Day 36* (± 5)	Day 43* (± 5)	Day 50* (± 5)	Day 57 (± 5)	1 month post open label phase † (± 5)
History/ Physical exam	X				X				X	
Zubrod score	X									X
Medication review	X	X	X	X	X	X	X	X	X	X
FACIT-F subscale, FACT-G, MFSI-SF, PROMIS-Fatigue, HADS, PSQI	X		X		X		X		X	X
ESAS	X	X	X	X	X	X	X	X	X	X
Physical Performance Tests (30 second chair stand test, six-minute walk test, accelerometer, Godin leisure-time PA questionnaire)	X				X				X	X
Body composition Body Mass Index (Bio Impedance), Resting energy expenditure using indirect calorimetry§	X				X				X	X
Cytokines (CRP, Serum IL-1b, TNF-α, IL-6; Intracellular cytokines IL-6 R; TNF R, IL- 1R, IL-10)	X				X				X	
Electrolytes liver function tests, PT/INR**, CBC**	X		X		X		X		X	X
Toxicity evaluation		X	X	X	X	X	X	X	X	X
Global Symptom Evaluation									X	

† patients in control arm and the intervention arm will have an option of treatment in drug or placebo +exercise arms

\*Assessment by phone or in person

\*\* PT/INR at baseline only unless patient is being treated with prophylactic anticoagulants. CBC at baseline only unless more frequently testing is clinically indicated.

-Assessments are performed by the Palliative Care team and complements the standard of care provided by the GI medical oncologists

## 7.2. Assessments

### 7.2.1 Physical Activity/ Function:

We will use the **30 second chair stand test**, six-minute walk test and an accelerometer. A self-report exercise questionnaire, the Godin leisure-time PA questionnaire, will be used to complement the objective measures. IM Systems-three dimensional accelerometers ("Biotrainer-Pro") will be used to objectively measure physical activity. These accelerometers complement the self-report for estimating PA and can record PA in 15-second increments for 5 days. Patients will wear the accelerometer for 5 days during the week before each assessment. When participants return the accelerometers the data will be uploaded into the project database, and the amount of time spent in moderate to vigorous activity will be calculated.

**30 second chair stand test:** The 30 second sit-to-stand task assesses lower body strength. A standard chair without arms with an approximate height of 17 inches will be used. After a demonstration, a practice trial of one repetition will be done to check for proper form. On the start signal, the participant rises to a full stand and then returns to a fully seated position. The patient completes as many full stands as possible within a 30 second period.

In the **six-minute walk test**, participants are asked to walk as fast and as far as they can for six minutes, and the distance walked is measured. The test will be conducted in an area with a 250 foot hallway and minimal traffic. The six-minute walk test has high test-retest and inter-tester reliability, and its validity is supported by correlations with self-report measures of fatigue and functional status. The patient will be strongly encouraged to give a maximum effort.

### 7.2.2 Patient-reported outcomes

**Functional Assessment of Cancer Illness Therapy (FACIT-F):** is a well-validated QOL instrument. This FACIT-F fatigue subscale was chosen as the primary outcome measure since it has been widely used in CRF treatment trials by our team and by others. The 13-item fatigue subscale is a patient-rated assessment of intensity of fatigue and its related symptoms on a scale of 0 to 4. This scale has been shown to have strong internal consistency ( $\alpha = 0.93-0.95$ ), sensitivity of 0.92, and specificity of 0.6923.

**Pittsburg Sleep Quality Index (PSQI):** This instrument provides a brief, clinically useful assessment of a variety of sleep disturbances that might affect sleep quality.

**Patient-Reported Outcomes Measurement Information System (PROMIS):** measures key symptoms and health concepts applicable to advanced cancer, enabling efficient and interpretable clinical trial research and clinical practice application of patient-reported outcomes (PROs). The PROMIS fatigue measure used in the study was found to be highly correlated with the legacy measures.

**Multidimensional Fatigue Symptom Inventory (MFSI-SF)** consists of 30 items designed to assess the multidimensional nature of fatigue. Ratings are summed to obtain scores for 5 subscales (general fatigue, physical fatigue, emotional fatigue, mental fatigue, and vigor).

**Hospital Anxiety Depression Scale (HADS):** This 14-item questionnaire has been validated in a number of clinical situations and has been widely used in medically ill patients.

**The Edmonton Symptom Assessment Scale (ESAS)** measures 10 common symptoms in the past 24 hours (pain, fatigue, nausea, depression, anxiety, drowsiness, shortness of breath, appetite, sleep, and feeling of well-being) during the previous 24 hours; This questionnaire has been found to valid and reliable in cancer populations.

Please see Table 4 for the timing of the assessments

**7.2.3. Cytokine assessments:** Peripheral blood will be collected at baseline, Day 29 and Day 57±5 (Table 4). On completion of the study, the change in levels of synthesis of cytokines in LPS-induced monocytes will be correlated with the proportion of patients with decreased fatigue and with those who have no decrease in fatigue. Methods: Briefly, 1 mL of peripheral blood will be incubated with 10 µg/mL LPS for 5 h and with brefeldin A for the last 3 h of incubation to block the intracellular transport of the de novo cytokine synthesis from the Golgi. Thereafter, LPS-activated monocytes will be stained for surface expression of CD14 and CD33 and for the presence of cytoplasmic cytokines, as previously described, by using a panel of cytokine-specific monoclonal antibodies conjugated with phycoerythrin to detect one of the cytokines. The cytokine assessments will be performed in [name] laboratory.

**7.2.4. Body Composition:** Cancer induced lean body mass loss/ fat loss occurs in a higher frequency in advanced cancer patients resulting in severe CRF, functional impairment and their inability to tolerate therapy. Resting energy expenditure, at baseline and Day 57±5. However all patients will be assessed for body mass index, phase angle evaluation using Bio electric impedance [Tanita bioelectrical impedance analysis body composition scale].

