**Prior Inflammatory cytokine and CRF studies by our team:**

Prior studies by our group showed wide variability in serum cytokine levels in patients with advanced cancer and hence the need to assess cytokines levels in LPS activated monocytes. PA results in modulation of TNF- $\alpha$ , IL-1 $\beta$ , and IL-6, interleukin-1 receptor antagonist (IL-1RA), TNF-receptors (TNF-R), and IL-10 levels. Since most of these factors are produced by activated monocytes/macrophages, we propose to assess the synthesis of these factors by resting (unstimulated) as well as LPS-activated peripheral blood monocytes isolated from patients before and after study treatment.

Figure 2 shows the synthesis of TNF- $\alpha$  by LPS-activated monocytes isolated from patients at baseline (D0) and at weeks 1- 5 after treatment with dexamethasone (DM). In patients treated with 8 mg DM daily (dark histograms), the percentage of LPS-activated monocytes that synthesized TNF- $\alpha$  decreased, whereas in patients receiving placebo (light histograms) for the first 2 weeks there was no change in the percentage of LPS-activated monocytes that synthesized TNF- $\alpha$  from D0 until week 2. Thereafter, when placebo patients (light histograms) switched to open-label DM, there was a decrease in the percentage of LPS-activated monocytes that synthesized TNF- $\alpha$ . Hence analyses of the levels of cytokines from induced monocytes would help to determine their association with change CRF and treatment, as shown in our previous studies.

**Change in TNF- $\alpha$  production by LPS-activated monocytes from dexamethasone-treated patients and placebo-treated patients in double-blind phase (Days 8 and 15) and in dexamethasone-only open-label phase (Days 29 and 35).**

**Figure 2. Monocyte Phenotype and LPS-induced cytokine synthesis.** (A) Monocytes are enumerated in whole blood as CD14\*SSCmid cells. (B) After a 4 hour incubation with LPS, the percentage of cell synthesizing cytokines can be enumerated. (C) TNF- $\alpha$  synthesis by monocytes decreases in patients treated with 8mg dexamethasone daily.

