#### Exercise Prescription.

For this study, we plan to use an exercise intervention based on the American College of Sports Medicine (ACSM) exercise recommendations for cancer survivors. The exercise intervention will include resistance training 3 days/week and moderate intensity walking for up to 150 minutes per week.

Participants will have weekly supervised (in person or by telephone) sessions with an ACSM-certified cancer exercise specialist. At the supervised, in person session the patient will perform the resistance exercise and moderate intensity walking up to 30 minutes, depending on the patient's tolerance.

The goal of the resistance exercises is to enhance the individual's ability to go from a seated to standing position independently. The resistance exercise program has been designed to strengthen the major muscles of the lower body, including the quadriceps, hamstrings, gluteus maximus, and hip flexor group.

These exercises will include (but will not be limited to) squats, lunges, leg extensions, leg curls, and hip extensions. We focus on the lower body to simplify the exercise plan, given the short timeframe of the intervention, and because lower body strength is critical to patient mobility and functioning. We will use resistance tubes as our mode of resistance. These tubes are color-coded to indicate their specific

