resistance level: light, moderate, or hard. The resistance exercise sessions are to be completed 3 days a week, allowing at least 48 hours between each session. This allows the muscles adequate time for rest and prevents overtraining. The participant will begin with 1 set of 10 to 12 repetitions at lightest resistance progressing to 2 sets of 12 repetitions as exercise tolerance increases. Resistance will then be increased as the participant's endurance and strength progresses. The graded resistance program will be designed so that the individual begins with a lighter resistance and progresses to heavier resistance once a level has been mastered. Since the level of aerobic fitness will vary among participants, the frequency and duration of the walking program will be established based on exercise physiologist's assessment of the participant's baseline aerobic fitness level (six-minute walk test). For example, the recommendation may be to walk 10 minutes 1-3 times a day or up to a 30-minute walk once a day at a moderate intensity level. Participants will work toward the goal of 150 minutes of moderate intensity walking per week.

To encourage and monitor adherence to the walking program, we will provide participants with a pedometer and an exercise log to record their resistance exercise sessions, time spent in moderate intensity walking, and the number of steps they take each day. Participants will be asked to walk a minimum of 5 days a week at the duration established by the exercise physiologist. In the first week of the intervention, the exercise physiologist will meet with each participant to evaluate his or her current strength and aerobic fitness level and to teach the assigned exercises. Each week the exercise physiologist will assess their progress and help them identify and overcome any barriers to completing the exercise program, and to evaluate for adverse events or health problems. The frequency, intensity, and duration of the assigned exercises will also be evaluated and adjusted as necessary.

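### With no exercise-free interval or test order set for the cytokine draws and resting-energy test, physical activity (PA) arm changes in these exploratory endpoints can mix recent exercise with the 8-week effect

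*Combined protocol and SAP*

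**What the plan says.** **Sampling.** Section 7.2.3 gives the cytokine schedule by visit only: "Peripheral blood will be collected at baseline, Day 29 and Day 57±5 (Table 4"). For calorimetry, section 7.2.4 says "Resting energy expenditure, at baseline and Day 57±5", while the Table 4 row containing "Resting energy expenditure using indirect calorimetry" is also marked at Day 29 and after the open-label phase.

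**Other tests at the same time points.** Table 4 marks "Physical Performance Tests (30 second chair stand test, six-minute walk test, accelerometer, Godin leisure-time PA questionnaire") at Baseline, Day 29 and Day 57, with no distinction by arm. Section 7.2.1 says of the six-minute walk: "The patient will be strongly encouraged to give a maximum effort".

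**Exercise in the PA arms (section 6.1, Exercise Prescription).** "Participants will be asked to walk a minimum of 5 days a week at the duration established by the exercise physiologist". Resistance work is on 3 days a week. The only spacing rule is 48 hours between resistance sessions, given for muscle rest. On supervision: "At the supervised, in person session the patient will perform the resistance exercise and moderate intensity walking up to 30 minutes". Nothing keeps this session apart from an assessment visit. Controls stretch only.

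**Link to the markers.** In section 1.4 the sentence beginning "PA results in modulation of TNF" goes on to name IL-1β, IL-6, IL-1RA, TNF receptors and IL-10.

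**Use of the data.** Secondary objective 3 is change in CRP and cytokines from before to after treatment. The Exercise Prescription text plans a comparison of the exercise and control programmes, and section 8 puts cytokines into a repeated-measures analysis of treatment.

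**The concern.** The baseline sample precedes the programme. At Day 29 and Day 57 an adherent PA-arm patient will usually have exercised recently, because the plan prescribes it; a control patient has been prescribed stretching. Randomisation does not remove this imbalance, since it is created by the assigned programme and by when the sample is taken.

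If the markers respond for some hours to a single session, the follow-up value carries that response as well as any lasting effect. Two analyses are exposed: the change from baseline within the PA arms, and the PA-versus-control difference. Section 7.2.3 also relates cytokine change to fatigue response. Adherent patients are more likely to have exercised recently and may also improve more, so an acute shift could be taken for a mechanism. The acute state cannot be recovered after the sample is taken.

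**Working it through.** **Step 0: the plan's own figure.** The plan states no figure for the cytokine or resting-energy endpoints. Its nearest figure is for the primary comparison (section 8): 30 per arm, effect size 0.65, two-sided 0.10, 80% power. Noncentrality is 0.65 × √(30/2) = 2.517, the critical t on 58 df is 1.672, and power is 80.0%. It reproduces, and the same formula is used below.

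**Step 1: exposure, from the prescription.** There are 21 ways to place 5 walking days in a 7-day week. In every one, exactly 5 of the 7 days follow a walking day: f = 5/7 = 71%. With one walk a day at a fixed hour, this is also the share of draws within 24 hours of the last walk. For resistance work alone the share is 3/7 = 43%. At baseline and in controls the *prescribed* share is 0.

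**Step 2: apparent shift.** Let a be the acute shift in SD units of the change score. The documents do not give it; 0.2, 0.35 and 0.5 are assumptions. With no lasting effect, the expected PA-versus-control difference is a × f:

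- 0.2 × 5/7 = 0.143 SD
- 0.35 × 5/7 = 0.250 SD
- 0.5 × 5/7 = 0.357 SD

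**Step 3: rejection probability.** Two-sample t-test, 30 per arm, two-sided 0.10 (the level of the primary test, assumed here), noncentrality a × f × √15:

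| Assumed acute shift | Noncentrality | Rejects |
|---|---|---|
| 0 | 0 | 10% |
| 0.2 SD | 0.553 | 15% |
| 0.35 SD | 0.968 | 25% |
| 0.5 SD | 1.383 | 39% |

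**Step 4: sensitivity to exposure.** Same formula, shifts of 0.2 / 0.35 / 0.5 SD:

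| Share of PA-arm draws shifted (controls 0) | Rejects |
|---|---|
| 43% (resistance sessions only) | 12% / 16% / 21% |
| 54% (5/7 × 0.75, scaling by the 75% adherence threshold in section 8; an assumption) | 13% / 19% / 27% |
| 71% | 15% / 25% / 39% |
| 100% | 20% / 38% / 61% |

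**Step 5: does a 24-hour gap fit the calendar?** Each 5-of-7 pattern leaves two days a week that follow a non-walking day. The Day 29 window (±3) spans 7 days and the Day 57 window (±5) spans 11, so such days fall inside both. Resistance sessions can use them up. Seven weekly patterns of 3 sessions avoid consecutive days. Paired with the 21 walking patterns this gives 147 combinations, of which 7 × 3 = 21 leave no day free of both. For those patients, and for anyone walking more than the minimum, sessions would have to be placed with the visit in mind.

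**The case against.** **The walk test is in every arm and at baseline.** This stands. A reader might infer that a maximum-effort walk beside the blood draw distorts the PA arms in particular. The documents do not support that: with a constant order its effect largely cancels in change scores and between arms. It matters only if the order varies. Nor does a shared Table 4 column prove one sitting, and section 7.2.6 lets a local physician draw the blood.

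**Baseline and control patients are not shown to be exercise-free.** This stands. Exclusion f removes only patients who do both frequent activity (30 minutes, 5 times a week) and strength training on 2 or more days. A daily walker who does no strength work is eligible. Zero exposure is true of the prescription, not necessarily of the patients, and background exercise would shrink the contrast.

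**The acute effect is undocumented.** This stands in part. Section 1.4 says PA modulates these markers, but the two studies it cites are, by title, of prolonged running and strenuous exercise. The trial prescribes moderate walking and graded tube resistance, and the assay described in detail is LPS-activated monocyte synthesis. No document gives the size or duration of an acute effect on it.

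**Activity is already recorded.** This stands in part. Accelerometers are worn for 5 days in the week before each assessment, and PA participants keep a log. But 5 days of wear need not include the day before the draw, the log as described holds sessions, walking minutes and steps rather than clock times, and no analysis uses either to qualify a sample.

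**Test conditions may be set elsewhere.** Possible. The appendices and any laboratory manual are not in the public text, nor is the Table 4 footnote on calorimetry.

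**Conclusion.** The point holds as a cheap improvement to exploratory secondary endpoints. As written, the plan lets recent exercise differ systematically between the PA arms at follow-up and both their own baseline and the control arm, for markers it says exercise modulates. The changes *can* mix acute and 8-week effects; the documents do not show that they do.

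On size, 71% of follow-up days come the day after a prescribed walk. Under assumed shifts of 0.2 to 0.5 SD, that exposure raises the chance of a spurious PA-versus-control finding from 10% to between 15% and 39%. These rates rest on full adherence, no comparable exercise in controls and a lasting effect of zero.

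Two stronger readings fail. A reader might infer that the trial's main result is compromised. It is not: icosapent plus PA and placebo plus PA share the same exercise prescription, so neither the primary FACIT-F comparison nor the drug contrast in cytokines is biased, although varying time since exercise may add noise to the latter. A reader might also take the 20%, 38% and 61% rates as the expected ones. They need every PA-arm draw shifted and no control draw, which the prescription does not imply.

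Separately, Table 4 and section 7.2.4 disagree on whether resting energy is measured at Day 29.

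**What to change.** 1. **Order of tests.** In sections 7.2.3 and 7.2.4 and in Table 4, state that at Baseline, Day 29 and Day 57 the blood draw and then calorimetry and impedance come before the performance tests and any supervised session.
2. **Interval.** In all arms and at all three time points, book the draw after a common exercise-free interval. Twenty-four hours is an example; the cut-off is assumed and should be settled with the laboratory. Apply it to draws by local physicians too.
3. **Record.** Note the date and time of last exercise at each draw, in every arm, supported by the existing logs and accelerometers. Flag draws that break the rule, and repeat the cytokine analysis without them.
4. **Reconcile** the resting-energy time points in Table 4 with those in section 7.2.4.

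Cost: a few lines of text, one extra item on the sample form, and slightly less flexible booking, with sessions placed around the visit for some patients. Sample size, the number of samples and the prescribed number of sessions do not change.

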This study is considered feasible if patient is adherent to the study. Adherence will be calculated as the mean of the percentage of total prescribed strength training sessions, the percentage of total prescribed walking regimen minutes completed (PA), and the mean (across all patients) percentage of total prescribed pills taken (study medication). The adherence rate, as defined, is a continuous variable. At the end of the study, we will estimate the average adherence of prescribed strength, of total prescribed walking regimen minutes and of total prescribed pills taken separately using mean, standard deviation, median, and range. This study intervention of combination of Icosapent Ethyl and Physical activity will be considered feasible as evidenced by adherence rate is  $>/=75\%$  to daily combined therapy during the 8-week intervention. The adherence rate can also be compared among all three groups using Kruskal-Wallis test. We will estimate 95% confidence intervals for the proportion of patients completing the intervention, the adherence rate, and the proportion of patients with a satisfaction over time. With 30 patients in each arm, a 95% confidence interval for a proportion of 73% (22/30), for example, can be estimated as (54%, 88%).

Data of variables of interest will be summarized using standard descriptive statistics, such as mean, standard deviation, median, and range for continuous variables, frequency and proportion for categorical variables. Correlation will be assessed among continuous variables using Pearson or Spearman correlation coefficient, whichever is appropriate. Association between categorical variables will be examined by Chi-Squared test or Fisher's exact test when appropriate. Boxplot and histogram will be applied to demonstrate distribution of variables of interest.

Since FACIT-F scores will be obtained at 0, 15, 29, 43 and  $57\pm 5$  days, and other QOL variables and cytokine markers will also be obtained repeatedly over time, we will also evaluate the effect of treatment on the changes of these measured over time using repeated measure analysis in which intra-

patient correlation of the measures are accounted for. However due to the small scale and exploratory nature of the study, we will report p-value as is without adjusting for multiplicity.

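### Section 7.2.3 ties cytokine change to a proportion of patients with decreased fatigue; a patient-level model of FACIT-F change, with a treatment-arm term, would be clearer and more efficient

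*Combined protocol and SAP*

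**What the plan says.** Section 7.2.3 (Cytokine assessments) sets the sampling: "Peripheral blood will be collected at baseline, Day 29 and Day 57±5". It then gives the analysis: the change in cytokine production by LPS-activated monocytes "will be correlated with the proportion of patients with decreased fatigue". The sentence goes on to name a second set of patients: "and with those who have no decrease in fatigue". It does not say which fatigue instrument defines a decrease, how large the decrease must be, whether the change runs to Day 29 or Day 57, which coefficient or test is used, or how treatment arm enters.

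The purpose is given in the account of the team's earlier cytokine studies in the introduction: "analyses of the levels of cytokines from induced monocytes would help to determine their association with change CRF and treatment".

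Section 8, repeated in the synopsis, has two general sentences that touch on this:
- "Correlation will be assessed among continuous variables using Pearson or Spearman correlation coefficient, whichever is appropriate". No variables are named.
- For FACIT-F, other quality-of-life measures and cytokine markers, "we will also evaluate the effect of treatment on the changes of these measured over time using repeated measure analysis". This concerns the effect of treatment on each measure, not the association between two measures.

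Section 8 adds that, because the study is small and exploratory, "we will report p-value as is without adjusting for multiplicity".

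Table 4 schedules FACIT-F at baseline and Days 15, 29, 43 and 57, and cytokines at baseline and Days 29 and 57. Every cytokine sample therefore has a FACIT-F score from the same visit.

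**The concern.** Section 7.2.3 is the only place that names an analysis linking cytokines to fatigue. Its two variables sit at different levels: a cytokine change is one value per patient, and a proportion is one value per group. The second half of the sentence suggests that a responder versus non-responder comparison is meant. That can be done, but it has three weaknesses.

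- It reduces a continuous score to yes or no, although the continuous change is available at the same visits.
- It leaves the definition of a responder open. Four fatigue measures are collected (FACIT-F, MFSI-SF, PROMIS-Fatigue and the ESAS fatigue item) and there are two post-baseline cytokine visits. That gives 4 × 2 = 8 definitions before any cut-off is chosen, with unadjusted p-values.
- It mentions no arm term. If treatment moves both fatigue and cytokines, an analysis that ignores arm can show an association where none exists within arms.

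At stake is the mechanistic question. The protocol criticises earlier fish oil work for not examining laboratory correlates, and draws blood three times per patient partly to answer this.

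**Working it through.** **1. Plan's own figure.** None is given for the cytokine analysis. The FACIT-F planning values used below come from section 8 (change 9.5 versus 3, SD 10, 30 per arm, two-sided 0.10). They reproduce the stated primary power: 6.5 / (10 × √(2/30)) = 2.517; 2.517 − 1.645 = 0.872; power about 0.81 by the normal approximation and 0.800 by the exact noncentral t, against the stated 80%.

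**2. Literal reading.** If the groups were the three arms, there would be three points. With 1 degree of freedom, |r| would have to exceed 0.997 (two-sided 0.05) or 0.988 (two-sided 0.10). The sentence does not mention arms, so this only shows why the literal reading is of no use.

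**3. Responder reading: efficiency kept.** Let the FACIT-F change be normal with mean μ and SD 10, jointly normal with cytokine change, and split at c. With z = (c − μ)/10 and responder proportion p = 1 − Φ(z), the correlation is multiplied by a = φ(z)/√(p(1 − p)), and the relative efficiency is a². The cut-offs are any improvement (c = 0) and the 10-point improvement that the introduction calls clinically relevant. Section 7.2.3 adopts neither.

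| Arm mean | Cut | z | p | a | a² |
|---|---|---|---|---|---|
| 9.5 | 0 | −0.95 | 0.829 | 0.675 | 0.455 |
| 3 | 0 | −0.30 | 0.618 | 0.785 | 0.616 |
| 9.5 | 10 | 0.05 | 0.480 | 0.798 | 0.636 |
| 3 | 10 | 0.70 | 0.242 | 0.729 | 0.532 |

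The efficiency kept is about 46% to 64%. The choice of cut moves the responder proportion from 83% to 48% in one physical activity arm and from 62% to 24% in the other.

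**4. Illustration of power.** The true correlation is not in the documents and is assumed here. So are 90 complete pairs (30 per arm × 3) and the test level, since none is stated for this analysis. The results come from 8,000 simulated trials per setting, drawn from a single population. The split range covers c = 0 with mean 9.5 or 3, and c = 10 with mean 9.5. The remaining case, c = 10 with mean 3, has an efficiency between these.

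| Assumed r | Continuous, 0.05 | Split, 0.05 | Continuous, 0.10 | Split, 0.10 |
|---|---|---|---|---|
| 0.2 | 0.48 | 0.24–0.33 | 0.60 | 0.35–0.44 |
| 0.3 | 0.82 | 0.48–0.63 | 0.89–0.90 | 0.62–0.74 |
| 0.5 | 1.00 | 0.91–0.98 | 1.00 | 0.96–0.99 |

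**5. Size of an arm effect, if arms were pooled.** Take two equal arms that differ by d₁ SD in fatigue change and d₂ SD in cytokine change, with no within-arm association. The pooled correlation is (d₁d₂/4) / √[(1 + d₁²/4)(1 + d₂²/4)]. The protocol's fatigue effect is d₁ = 0.65. The cytokine effect is an assumption.
- d₂ = 0.65: 0.1056/1.1056 = 0.10.
- d₂ = 1.0: 0.1625/√(1.1056 × 1.25) = 0.14.

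This is modest, but not negligible beside a true correlation of 0.2 to 0.3.

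**The case against.** The strongest reply is that the sentence is clumsy rather than wrong. It names two sets of patients, and comparing cytokine change between them is an ordinary analysis once a cut-off is set. Section 8 already permits Pearson or Spearman correlation of continuous variables and analyses FACIT-F and cytokines as repeated measures. A cytokine–fatigue association is not a listed objective: secondary objective 3 concerns the effect of the intervention on cytokines and is exploratory.

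Much of this stands, and it rules out several stronger readings that a reader might infer:

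- **That the analysis cannot be computed.** Only the literal pairing fails. The responder comparison can be run once its definition is supplied.
- **That the plan throws away the continuous FACIT-F change.** Section 8 leaves room for a continuous analysis. The loss applies to the method that section 7.2.3 states.
- **That the plan pools the arms and so confuses mechanism with treatment.** The text is silent on pooling, stratifying and adjusting, and the stated purpose mentions treatment. The gap is the missing arm term, not a stated decision to pool.
- **That a particular loss of power is a property of this trial.** The documents give no correlation, test level or expected number of complete pairs for this analysis.

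What does not stand is that section 8 settles the matter. Its correlation sentence names no pair, and its repeated-measures analysis asks about treatment effects. The only sentence specific to cytokines and fatigue still points to a different and less efficient method.

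**Conclusion.** The point holds as a minor, cost-free improvement. Section 7.2.3 should name a patient-level analysis and agree with section 8. In its workable reading it leaves the responder definition open, mentions no arm term, and keeps about 46% to 64% of the efficiency of the continuous FACIT-F change, a loss of about 36% to 54%.

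That range rests on the protocol's means and SD for the two physical activity arms, on bivariate normality, and on the two illustrative cut-offs. The documents assume no FACIT-F change for the third arm. The power figures are illustrations only: at two-sided 0.05 with 90 complete pairs, the loss is material for assumed correlations of 0.2 to 0.3 and small at 0.5. Neither the primary comparison nor the sample size depends on this analysis.

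**What to change.** Replace the sentence in section 7.2.3 with wording such as: for each cytokine, the change in FACIT-F fatigue subscale from baseline to Day 57 will be modelled by linear regression on the change in that cytokine over the same interval, adjusted for treatment arm and for the baseline FACIT-F and cytokine values; an arm-adjusted (partial) or within-arm Spearman correlation will be reported in support.

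An unadjusted Spearman correlation across all patients would not do as the support, because it ignores arm.

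If a responder comparison is kept as a supplement, state its instrument, time point and cut-off in advance. Name the cytokines to be analysed, since secondary objective 3 and Table 4 list the intracellular markers differently. Add a matching line to section 8 so that the two sections describe one analysis.

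The cost is a few lines of text. No new data, visits or patients are needed.
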